5.3. Other Data to be Assessed

Other data for this study include, but are not limited to:

- Overall patient survival post cryoablation;
- Time to metastatic lung disease progression beyond the index tumor(s);
- Time to overall cancer progression;
- Time to untreatable metastatic lung disease control with cryoablation;
- Time to untreatable metastatic lung disease control with focal therapy;
- Efficacy of cryoablation on local tumor control for each index tumor in patients with pulmonary metastatic disease at 18 and 24 months post cryoablation;
- Efficacy of cryoablation on local tumor control for each index tumor in patients with pulmonary metastatic disease undergoing additional cryoablation treatment(s) of a previously treated index tumor;
- Cryoablation technical success (See Section 10.5.5);
- Changes in physical function and quality of life over time (See Section 10.5.5).

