7.9. Study Completion or Withdrawal

Patients may withdraw from this study at any time, with or without a reason, without prejudice to further treatment. Investigators should make every effort within the bounds of safety and patient choice to have each patient complete the study. If a patient does not return for a scheduled visit, every effort should be made to contact the patient. In any circumstance, every effort should be made to document patient outcome, if possible. The investigator should inquire about the reason for withdrawal; request the patient return for a final visit, if applicable, and follow-up with the patient regarding any unresolved adverse events. If possible, the reason(s) for withdrawal (if given) will be recorded.

If the patient withdraws from the study and also withdraws consent for disclosure of future information, no further evaluations should be performed and no additional data should be collected. The sponsor may retain and continue to use any data collected before such withdrawal of consent.

Patients who request Early Termination from the study will be asked to return if physically capable for a final visit to complete the following assessments.

- Karnofsky Performance Scale;
- Chest CT scan, \pm contrast (contrast is preferred);
- Safety assessment;
- Assessment of metastatic lung disease progression, including additional treatment;
- Assessment of any new cancer treatment(s).

In the event the patient enters hospice or another similar care program, early termination should be documented. Information taken from the medical record is sufficient to document this reason for early termination in the event this communication is not provided by the patient.

Patients may be considered "lost to follow-up" after 3 unsuccessful attempts to contact the patient with one contact being a registered letter to the last known address of the patient. Site should document all attempts to contact the patient in the source documents.

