10.5.5. Other Data Assessments

Technically successful treatment definition

A technically successful treatment will be defined by the presence of an ablation zone, ground glass opacity, or frank consolidation encompassing the targeted index tumor(s) no later than the 1 month follow up visit after the cryoablation procedure. Technical success will be analyzed on a per tumor basis.

Disease recurrence or progression definitions

The reference date for disease progression evaluation will be associated with the initial (first) cryoablation procedure done per study protocol. In the event of multiple cryoablation procedure dates, such as with bilateral lesions or staged treatments, the date of reference for disease progression evaluation will be the initial (first of n) cryoablation procedure.

- **Local disease progression** will be determined locally by evidence of local tumor failure.
- **Lung-disease-specific survival rate** is defined as the time in days from the first cryoablation procedure to death and **a)** the date of metastatic lung tumor progression (new lung tumors or local tumor failure of the index tumor), **b)** the date of death with local control of the index tumor, or **c)** the date of last follow up in patients who were still alive with local tumor control of the index tumor. Patients who are alive will be censored at the date of their last visit. Patients who have died from causes other than local failure of the index tumor will be censored at the time of death. Lung disease-specific survival rates will be summarized by using Kaplan-Meier methodology.
- **Overall survival rate** is defined as the time in days from the first cryoablation procedure to death. Patients who are alive will be censored at the date of the last visit. Overall survival rates will be summarized by using Kaplan-Meier methodology.
- **Time to metastatic lung disease progression beyond the index tumor** is defined as the time in days from the first cryoablation procedure to metastatic disease beyond the index tumor site. Patients without metastatic lung disease progression will be censored at the date of their last visit or their date of death (due to any cause). Metastatic progression free survival rates will be summarized by using Kaplan-Meier methodology.

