Efficacy of cryoablation on local tumor control for each index tumor in patients with pulmonary metastatic disease undergoing additional cryoablation treatment(s) of a previously treated index tumor will be summarized using the proportion of tumor control at 12-months post re-treatment and a 95% CI.

Technically successful treatment

A technically successful treatment will be defined by an ablation volume, ground glass opacity, or frank consolidation encompassing the targeted index tumor(s) within 30 days of the cryoablation procedure. Technical success will be calculated on a per-tumor level as well as a patient level. To be considered a technical success on a patient level all tumors treated during the baseline procedure must meet the technical success criteria. Technical success rates and 95% CIs will be calculated using random effects logistic regression on a tumor level and logistic regression on a patient level.

Disease recurrence or progression

The reference date for disease progression evaluation will be associated with the initial (first) cryoablation procedure done per study protocol. In the event of multiple cryoablation procedure dates, such as with bilateral lesions or staged treatments, the date of reference for disease progression evaluation will be the initial (first of n) cryoablation procedure.

- **Local disease progression** will be determined locally by evidence of local tumor failure. Time to lung disease progression will be summarized by using Kaplan-Meier methodology.
- **Lung-disease-specific survival** rate is defined as the time in days from the first cryoablation procedure to death and **a)** the date of lung tumor progression (new lung tumors or incomplete response), **b)** the date of death without lung tumor progression, or **c)** the date of last follow up in patients who were still alive without lung tumor progression. Patients who are alive will be censored at the date of their last visit. Patients who have died from causes other than lung cancer will be censored at the time of death. Lung disease-specific survival rates will be summarized by using Kaplan-Meier methodology.
- **Overall survival** rate is defined as the time in days from the first cryoablation procedure to death. Patients who are alive will be censored at the date of the last visit. Overall survival rates will be summarized by using Kaplan-Meier methodology.

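### Capture of deaths after hospice entry rests on a best-effort request, so deaths that go unrecorded would be censored and would bias Kaplan-Meier overall survival upward

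*Protocol*

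**What the plan says.** Protocol section 7.9 (Study Completion or Withdrawal) makes hospice entry an early termination: "In the event the patient enters hospice or another similar care program, early termination should be documented". No patient contact is needed to record it: "Information taken from the medical record is sufficient to document this reason for early termination". The same section contains a general request, "In any circumstance, every effort should be made to document patient outcome, if possible", and stops data collection only in one case: "If the patient withdraws from the study and also withdraws consent for disclosure of future information".

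Protocol section 10.5.5 says that overall survival "is defined as the time in days from the first cryoablation procedure to death. Patients who are alive will be censored" at the last visit, and that "Overall survival rates will be summarized by using Kaplan-Meier methodology". The SAP, under Disease recurrence or progression, repeats the rule: "Patients who are alive will be censored at the date of the last visit". Overall survival is the first item in protocol section 5.3 ("Overall patient survival post cryoablation"), a list of other data with no hypothesis or performance goal attached.

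**The concern.** Kaplan-Meier treats a censored patient as having the same future risk as those still followed. A patient who has just entered hospice does not: death is usually near. If that patient is terminated alive and the death is never recorded, the analysis sees a living patient at the last visit and drops a death that was about to happen.

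Nothing else in the plan is certain to catch such deaths:

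- The final-visit assessments in section 7.9 and the withdrawal column of Table 1 have no vital-status item, and no contact is scheduled after termination.
- Protocol section 13 records adverse events only when they occur within 30 days of the procedure, so a later hospice death need not be reported through safety.
- The missing-data sensitivity analyses (protocol section 10.2; SAP, Handling of Missing Data) concern the primary efficacy endpoint only.

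Lung-disease-specific survival also censors living patients at their last visit, so it has the same exposure. At stake is how far the survival curve can be trusted in patients with stage 4 disease followed for 24 months.

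**Working it through.** **Plan's own figures.** The documents give no planned figure for overall survival. The only design calculation is for the primary endpoint. It reproduces: with rejection at 181 or more of 203 tumors, exact alpha is 0.02388 and power 0.85008 (stated 0.0239 and 0.8501), and 203/0.9 rounds up to 226. None of these uses overall survival.

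**Inputs from the documents.** Protocol section 3.2 cites 1-year survival of 91% and 3-year survival of 59.6% in a 24-patient colorectal-metastasis series, and 1-year survival of 89.4% in a 20-patient metastatic series. Follow-up runs to 24 months, with about 150 patients expected.

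**Assumptions not in the documents.** Let g be the share of deaths that both follow hospice entry and go unrecorded. I take g = 10%, 25% and 50%, constant over time, with no other censoring before 24 months.

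**Formula.** If a share g of deaths is turned into censoring, Kaplan-Meier sees only a fraction (1 − g) of the hazard, so

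apparent S(t) ≈ [true S(t)]^(1 − g).

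**True 24-month survival under each anchor.**

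- 1-year 91%, constant hazard: 0.91² = 0.828.
- 1-year 89.4%, constant hazard: 0.894² = 0.799.
- 3-year 59.6%, constant hazard: h = −ln(0.596)/3 = 0.1725 per year; exp(−2 × 0.1725) = 0.708. This implies 1-year survival of exp(−0.1725) = 84%, against the 91% cited for the same series.
- Both points joined: 0.91 × √(0.596/0.91) = 0.736.

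**Apparent 24-month survival from the formula.**

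| Anchor | True | g = 10% | g = 25% | g = 50% |
|---|---|---|---|---|
| 1-year 91% | 82.8% | 84.4% | 86.8% | 91.0% |
| 1-year 89.4% | 79.9% | 81.7% | 84.5% | 89.4% |
| 91% and 59.6% joined | 73.6% | 75.9% | 79.5% | 85.8% |
| 3-year 59.6% | 70.8% | 73.3% | 77.2% | 84.2% |

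**Simulation check.** Kaplan-Meier curves were simulated with exponential survival and a mean of 1 month from hospice entry to death. Lost patients were censored at their last scheduled visit. The 91% anchor gave 84.5%, 86.7% and 91.1%, and the 89.4% anchor gave 81.6%, 84.4% and 89.1%.

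**What drives the bias.** Censoring at the hospice date instead of the last visit moved the simulated result by only about 0.1 point. The bias therefore comes from uncaptured deaths and not from the choice of censoring date. With 50% of deaths preceded by hospice and half of those captured (net g = 25%), 24-month survival under the 91% anchor was 86.8% instead of 91.1%, so the bias roughly halves.

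**Scale in patients.** With 150 patients and 82.8% survival, 150 × 0.172 ≈ 26 deaths are expected by 24 months. Losing 10% of them means 2 or 3 missed deaths, and losing 50% means 13.

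**The case against.** A reader might infer that hospice patients are removed from the survival analysis by rule, and that survival is therefore certainly overstated. The documents do not support that. Overall survival is time to death and only living patients are censored, so a recorded death after hospice entry is an event. Neither document makes hospice entry or early termination a censoring event in itself. Section 7.9 asks for outcome to be documented in any circumstance and ends data collection only when consent for disclosure is also withdrawn. Protocol section 10.2 and the SAP use whatever data exist on patients who drop out, and the SAP counts deaths in subject disposition. All of this stands, and it makes the point conditional.

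A reader might also blame the last-visit rule itself. The 0.1-point result above shows that it is not the source of this bias.

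Nor can any row of the table be read as an expected effect. Each supposes a share of lost deaths that the documents do not state, and the anchors come from small series and disagree with one another. Overall survival has no hypothesis, comparator or power, and its place at the top of section 5.3 is list order and not a ranking.

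What the objection does not remove is the gap in procedure. The request to document outcome names no data item, time point, source or duration, and does not say that outcome means vital status. Using available data does not oblige anyone to obtain them.

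**Conclusion.** The point holds in conditional form. The plan ends participation at hospice entry, leaves later deaths to best effort, and has no overall-survival analysis that tests the resulting censoring. Deaths missed after hospice entry bias the Kaplan-Meier estimate upward; deaths that are recorded do not.

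The size cannot be fixed from the documents. Across the four anchors, the formula puts the overstatement at 24 months at about 1.6 to 2.5 points if 10% of deaths are lost, 4.0 to 6.4 points at 25%, and 8.2 to 13.4 points at 50%. These figures assume a constant lost share and no other censoring. With full capture this bias is zero. The primary test, its alpha, power and sample size do not depend on overall survival. A correction is worth making because the error has a known direction and costs little to prevent.

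**What to change.** In protocol sections 7.9 and 10.5.5 and in the SAP's overall survival definition:

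1. Require vital status and date of death to month 24 for every treated patient who has not withdrawn consent for disclosure, including after hospice entry or any other early termination. Collect them from the medical record or by telephone at the existing visit times; note i to Table 1 already allows telephone follow-up.
2. State that these deaths are events, and censor living patients at the last date known alive. The two changes belong together. If later deaths were counted while survivors were still censored at their last visit, ascertainment would be uneven and could bias survival downward.
3. Add one overall-survival sensitivity analysis that treats hospice terminations with unknown vital status as deaths at or shortly after termination.

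The cost is new wording in both documents, a small amount of extra site contact and one extra analysis. Sample size, alpha and power do not change.

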7.10. Pertinent Concurrent Medications

Data will be collected regarding concurrent pertinent medication taken at the time of screening and through 30 days post procedure. In the event of multiple cryoablation procedures, the pertinent medications will be followed through 30 days of the last procedure. Any medication which could affect the outcomes of this study should be included. Examples of pertinent medication include any medication taken for the following indications:

- Treatment of cancerous tumors within the lung;
- Improve/affect lung function (including cough);

- Anticoagulation therapy;
- Antiplatelet therapy.

Medications recorded at screening which are prescribed for coagulopathy or bleeding disorders must appropriately wash out before the cryoablation procedure according to the investigator's standard of care. These medications include, but are not limited to, warfarin (e.g. Coumadin), clopidogrel (e.g. Plavix), Phenindione (e.g. Dindevan) and aspirin. Herbal supplements with blood thinning properties should also be washed out appropriately.

Supplemental treatment which, in the investigator's opinion, becomes necessary during the course of the study must not be denied to the patient. If this supplemental treatment is described as a therapy expressly not permitted or which may affect the primary efficacy outcome, the patient's participation in the study will need to be discontinued due to non-permitted concurrent therapy.

8. ASSESSMENTS

8.1. Demographics

Demographic information will be collected from the patient during screening. The information will consist of age at the date of consent, race and sex. Per French regulations, race and ethnicity will not be collected at any study site in France.

8.2. Targeted Medical History

Targeted medical history information must be obtained from each patient entering the study. Obtaining accurate medical history is necessary to ensure documented baseline health status and to ensure that patients meet study entry criteria.

8.3. Laboratory Tests

Laboratory tests will be performed by the site's local laboratory. The following laboratory tests are required within 8 weeks of the initial cryoablation procedure.

- Platelet Count;
- ANC;
- INR.

8.3.1. Biopsy

A biopsy of a tumor(s) in the lung(s) metastasized from another primary disease may be obtained at the discretion of the treating investigator per his/her standard practice.

8.4. Physical Performance

Physical function assessments will be measured using Karnofsky Performance Scale (KPS).

Karnofsky Performance Scale (KPS)

The Karnofsky Performance Scale is a standard way of measuring the ability of cancer patients to perform ordinary tasks. The scores range from 0 to 100. A higher score means the patient is better able to carry out daily activities. KPS may be used to determine a patient's prognosis, to measure changes in a patient's ability to function. (See Appendix D)

KPS will be assessed at screening and months 1, 3, 6, 12, 18, and 24.

8.5. Quality of Life

To measure quality of life, this study will use the Short Form (SF)-12 generic measure.

SF-12 will be completed by the patient at screening, month 1 and month 3. (See Appendix F) In the event the month 1 or month 3 visit is missed, the SF-12 should be completed at the first two follow-up visits, regardless of the visit interval.

Short Form – 12 (SF-12)

The SF-12 is a shortened version of the well-known SF-36. The SF-12 assesses eight domains (physical functioning, role limitations due to physical health problems, bodily pain, social functioning, and general mental health, role limitations due to emotional problems, vitality and general health perception).

8.6. Imaging

The tumor(s) intended for ablation is referred to as the **index tumor(s)**. Index tumor evaluation will be conducted with the use of CT or FDG-PET-CT. The same method of assessment and the same technique should ideally be used to characterize each identified and reported index tumor at baseline and during follow-up. Imaging shall be performed with a minimum slice thickness of 5 mm and high resolution imaging is preferred with slice thickness of 3 mm or less. Three axes of measurements (longest diameter and the 2 perpendicular diameters) shall be evaluated and the longest dimension shall be used to determine the inclusion criteria. The use of contrast is preferred.

The cryoablation procedure will be completed under CT guidance. Week 1 follow-up imaging will be either chest CT or chest X-Ray. At months 1, 3, 6, 12, 18, and 24, follow up imaging will be chest CT or chest FDG-PET-CT.

The total area treated with cryoablation will be referred to as the **ablation zone(s)** in follow up imaging studies.

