6.2. Inclusion Criteria

Eligible patients for this study must meet all of the following criteria:

- 6.2.1. Patient must be at least 18 years old.
- 6.2.2. Patient has signed a written informed consent.
- 6.2.3. Patient presents with Stage 4 pulmonary metastatic disease with metastatic disease previously confirmed by prior biopsy;
or
Patient presents with Stage 4 pulmonary metastatic disease previously confirmed on imaging (e.g. CT) with histology proven primary cancer.
- 6.2.4. Patient has up to 6 local pulmonary metastases targetable by cryoablation.
- 6.2.5. Targeted index tumor(s) defined as intra pulmonary or pleural with a maximum size of 3.5 cm, measured in the longest cross sectional dimension.
- 6.2.6. The target index tumor(s) is determined (by CT images) to be in a location where cryoablation is technically achievable based on the proximity of adjacent organs/ structures and is greater than 0.5 cm from any critical organ/structure (possibly achieved with additional maneuvers such as iatrogenic pneumothorax or hydrodissection).
- 6.2.7. Karnofsky Performance Scale (KPS) score ≥ 60 .
- 6.2.8. Platelet count $>50,000/\text{mm}^3$ within 8 weeks prior to initial cryoablation procedure.
- 6.2.9. INR <1.5 within 8 weeks prior to initial cryoablation procedure.
- 6.2.10. Patient has a life expectancy of >3 months.

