8.7. Response Determination

The month 1 post-ablation CT examination will be used as the reference for determining index ablation zone response at each follow up interval after cryoablation. Sequential follow up intervals will be used to determine local failure.

In the unforeseen circumstance where the patient is unable to complete imaging according to the month 1 follow up visit, the month 3 imaging study may serve as the reference for determining index tumor response at each follow up interval after cryoablation. Every effort should be made to comply with the month 1 imaging requirement.

Efficacy at 12 months post cryoablation will be based on local tumor control that will be separately assessed for each index tumor according to criteria below. Each ablation zone will be evaluated at each time point by measuring its 3 axes (longest diameter and the two perpendicular diameters). For each ablation zone individually, the sum of these three measures will be compared to the 1 month baseline for tumor response and the previous follow up interval imaging study for local failure.

Each ablation zone measurement assessment, along with the overall clinical evaluation of the patient, will be evaluated by an independent imaging panel to assess the final response determinations. This final review can be used in the analysis in the event of 'indeterminate' imaging measurement assessments.

Local Tumor Control will be defined as the absence of local failure.

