8.7.4 Local Failure

Local failure will be defined as $\geq 20\%$ increase in the sum of the three axes of measurements (longest diameter plus the two perpendicular diameters) when compared with the nadir of this 3 axes measurement.

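### The CT acquisition rule in Protocol 8.6 contradicts itself: it sets a 'minimum' slice thickness of 5 mm while preferring 3 mm or less, so no upper limit is stated for the scans behind the primary endpoint

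*Protocol*

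**What the plan says.** Protocol section 8.6 gives the acquisition rule in one sentence with two halves: imaging is to be "performed with a minimum slice thickness of 5 mm and high resolution imaging is preferred with slice thickness of 3 mm or less". The first half is binding; the second is a preference. The same section asks that method and technique ideally be kept constant for each tumor, and takes the longest of three measured axes as the size for inclusion. Section 6.2 admits tumors "with a maximum size of 3.5 cm, measured in the longest cross sectional dimension".

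These scans also produce the primary endpoint. Under section 8.7 each ablation zone is measured on three axes, the longest diameter and two at right angles to it, and the three are summed. Section 8.7.4 calls local failure when that sum rises by 20% or more "when compared with the nadir of this 3 axes measurement". Section 8.7 then states: "Local Tumor Control will be defined as the absence of local failure".

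No upper limit on slice thickness appears in Table 1, the visit descriptions in sections 7.5 to 7.7, the response criteria in section 8.7, the central imaging review in section 16.2, or the SAP.

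**The concern.** A minimum thickness of 5 mm means 5 mm or thicker. On that reading the preferred scans do not comply, and a series of 7 or 10 mm does. A monitor or central reader checking a scan against the written rule would find no figure on which to query a thick series.

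Some variation in acquisition can be foreseen. Section 5 plans about 15 sites in the United States and elsewhere, and section 7.2 accepts routine scans taken before consent for screening. What is at stake is the consistency of a measurement judged against a fixed percentage threshold. If one axis is resolved only to about one slice, a thick slice can make up a large share of a small sum, and could create a failure or hide one.

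**Working it through.** **The plan's own figures.** The plan gives no calculation for slice thickness. The design figures for this endpoint reproduce: with 203 tumors and rejection at 181 or more successes, the exact one-sided binomial gives alpha 0.02388 at 84% (stated 0.0239) and power 0.85008 at 91% (stated 0.8501); 203 / 0.90 = 225.6, rounded up to 226. None of these depends on slice thickness.

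**The two halves of the rule.** Required: thickness ≥ 5 mm. Preferred: thickness ≤ 3 mm. The two sets do not overlap. If 5 mm is read as a maximum, the preferred set lies inside the required one and the sentence is consistent.

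**Illustration of size.** Inputs from the protocol: the three-axis sum (8.7), the 20% threshold against nadir (8.7.4), the 3.5 cm size limit (6.2) and the planned 5 mm margin (7.3.3).

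Assumptions not in the documents: all three axes equal a diameter D at nadir; only one axis is affected; its error is one slice thickness s. The 10 mm slice and the 10 and 15 mm zones are also chosen for illustration.

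- Sum = 3D. Failure threshold = 0.20 × 3D = 0.6D.
- Error as a share of the sum = s / 3D.
- Largest zone: 35 mm tumor + 2 × 5 mm margin = 45 mm, sum 135 mm.

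| Zone D (sum) | s = 3 mm | s = 5 mm | s = 10 mm |
|---|---|---|---|
| 10 mm (30 mm) | 10.0% | 16.7% | 33.3% |
| 15 mm (45 mm) | 6.7% | 11.1% | 22.2% |
| 45 mm (135 mm) | 2.2% | 3.7% | 7.4% |

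The diameter at which the error alone equals the threshold is D = s / 0.6, which is 5.0, 8.3 and 16.7 mm for slices of 3, 5 and 10 mm. If the error were two slices, these diameters would double to 10.0, 16.7 and 33.3 mm.

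**Shrinkage.** The comparator is the nadir, so a zone that starts large may be small when it counts. If the 45 mm zone falls by 75%, the complete-response limit in section 8.7.1, its sum is 0.25 × 135 = 33.75 mm and the failure threshold is 0.20 × 33.75 = 6.75 mm. One slice is then 8.9% of the sum at 3 mm, 14.8% at 5 mm and 29.6% at 10 mm.

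**The case against.** The strongest reply is that this is a slip of wording. By calling 3 mm or less preferred and high resolution, the sentence shows that thinner is better, so 'minimum' must mean a minimum standard. That largely stands. A reader might infer that the protocol excludes the preferred scans, but the stated preference speaks against it. What remains is that the binding half is wrong as written and nothing elsewhere corrects it.

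A reader might also infer that compliant scans are in general too thick to judge a 20% change. The documents do not support that. No figure for measurement error is given, and a 45 mm zone stays at 7.4% even with 10 mm slices under the one-slice assumption. At 5 mm, the probable intended limit, the 10 and 15 mm zones also stay below 20%. Nor do the documents say that any site used slices above 5 mm, or that one of the three axes runs along the scan direction. The cross-sectional size in section 6.2 can be read as an in-plane measurement, which slice thickness would affect less; no effect on eligibility is calculated here.

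Third, section 8.7 sends measurements to an independent imaging panel and section 16.2 adds central review by experienced radiologists. They need not accept an unreadable scan. This is a partial safeguard: neither section sets a thickness limit, and a second reading cannot restore resolution the scan lacks.

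Finally, a reader might conclude that the trial's error rates or power are compromised. Nothing supports this, because the documents do not show how many thick-slice scans there were, if any.

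**Conclusion.** The rule is wrong as written and should be corrected. It is a minor point: a contradiction in one sentence, probably meant as a maximum of 5 mm and likely to be read that way at most sites. It deserves correction because the sentence governs the scans for eligibility size and the primary endpoint, and no other text supplies the missing limit.

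On the one-slice, equal-axis assumption, a 10 mm slice could by itself reach the local-failure threshold only in zones of about 17 mm or less at nadir, and a 5 mm slice only in zones of about 8 mm or less. A larger assumed error raises those diameters, as the two-slice figures show. Alpha, power and sample size are unaffected.

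**What to change.** In section 8.6, replace the required minimum with a maximum slice thickness of 5 mm, keeping 3 mm or less as the preference. Add a slice-thickness field to the imaging eCRF, so that any scan above 5 mm can be identified and, if there are any, their influence on the primary endpoint examined.

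Leave the existing wording on consistent technique as an ideal. Mandatory matching of thickness to each tumor's reference scan would be a new acquisition requirement at every site through 24 months, which this error does not call for.

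The cost is one word in a protocol amendment and one eCRF field. The SAP revision history shows that patients had already been enrolled by its January 2017 entry, so the field would have to be back-filled for scans already taken.
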